3.1 Primary Efficacy Endpoint

The primary efficacy endpoint is the mean change in weekly mean Worst Itch Numeric Rating Score (WI-NRS) recorded in the subject's diary from Baseline to Week 12 for MC2-25 cream compared to MC2-25 vehicle. Weekly mean WI-NRS is calculated as the average of all and at least 4 non-missing WI-NRS values recorded in the subjects' diaries for the 7 days prior to and including the scheduled in clinic visits (8 days in total expected). If less than 4 observations are recorded in the 8 days expected, the weekly mean WI-NRS will be considered missing.

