7.9.1 Worst itch numeric rating score (WI-NRS)

The subject's WI-NRS must be recorded by the subject in a diary once daily (at the same time of the day throughout the trial, i.e., morning, afternoon, or evening for all recordings) on day -7 to day 0 (where day 0 = next on-site visit day) leading up to each visit (8 days in total) at Baseline, Week 1, Week 4, Week 8, and Week 12 or Early Termination using an 11-point numeric rating scale ranging from 0 to 10:

Please score the intensity of the Worst Itch you have experienced in the past 24 hours: 0 (no itch), 1, 2, 3, 4, 5, 6, 7, 8, 9, 10 (very severe/extreme itch).

In addition, the subject's WI-NRS must be evaluated at on-site visits at Screening, Baseline, Week 1, Week 4, Week 8, and Week 12 or Early Termination using the 11-point verbal rating scale above.

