8.8.1 Primary endpoint

The primary endpoint, mean change in weekly mean WI-NRS recorded in the subject's diary from Baseline to Week 12 for MC2-25 cream compared to MC2-25 vehicle, will be analysed by a mixed model of repeated measures with Baseline weekly mean WI-NRS as covariate and treatment, CKD stage stratum at baseline, systemic CKP-aP treatment status at baseline and visit as fixed factors with a two-sided α =0.05. The weekly mean WI-NRS is calculated as the average of minimum 4 WI-NRS values recorded once daily in the subject's diary from 7 days prior to and including the visit days (i.e., must be recorded for 8 days total).

On the FAS, the primary analysis and one sensitivity analysis will follow a treatment policy strategy irrespective of any potential intercurrent events. On primary analysis, missing values will be replaced following a multiple imputation procedure adequate for the endpoint assuming missingness appearing at random and based on 20 imputations. On the FAS, sensitivity analyses will include imputation by last observation carried forward (LOCF; treatment policy strategy) and multiple imputation of missing data and all data after start of rescue medication (hypothetical strategy).

Applying the same statistical model, further estimands include multiple imputation on the MFAS and as observed on the PPS, both following a treatment policy strategy. If deaths occur, further estimands may be defined following a composite endpoint strategy.

Supportive subgroup analyses will be conducted by dialysis status and CKD stages and by country on the FAS.

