- 4. Phone calls: To remind subjects about diary documentation (in particular once-daily WI-NRS assessments that must be performed for 8 days leading up to each on-site visit [i.e., from day -7 to day 0 where day 0 = next on-site visit day]) and to ask for AEs. Phone visits may be replaced by in-clinic visits where relevant, e.g., in subjects going to the dialysis unit for haemodialysis.
- 5. Informed consent must be signed by both subject and investigator before any trial-related procedures are performed.
- 6. At-home (diary) assessments must be performed for 8 days leading up to each visit, i.e., from day -7 to day 0 where day 0 = next on-site visit day.
- 7. The WI-NRS must also be reported by the subject at on-site visits
- 8. At all on-site visits, all patient-reported outcome (PRO) assessments should be completed before all other clinical assessments or procedures.
- 9. The trial staff must estimate the % body surface area treated based on the subject's indication of CKD-aP treatment area size on the CKD-aP treatment area diagram.
- 10. Physical exam: A complete physical examination is required at Screening and Week 12 (EoT or Early Termination) visits. An abbreviated physical examination is required at the Baseline visit (and if judged necessary by the investigator) at the FU visit if the FU visit is applicable.
- 11. Vital signs include blood pressure, heart rate, and body temperature measurement. For subjects on haemodialysis vital signs are to be assessed prior to dialysis. Blood pressure and pulse rate will be taken with the subject in the sitting position with approximately 5 minutes rest prior to measurement.
- 12. Serum pregnancy tests are conducted for women of childbearing potential. At Baseline a urine pregnancy test must also be conducted except for dialysis subjects with anuria.
- 13. For subjects on dialysis, the blood samples must be collected before dialysis.

MC2 Therapeutics Protocol No- MC2-25-C1 V3.0 SAP Final V1.0

- 14. Only at selected sites and only for subjects who have provided additional consent. CKD-aP target area selected at Baseline. Images of CKD-aP target area must be taken before tape stripping and skin biopsies.
- 15. Only at selected sites and only for subjects who have provided additional consent. Biopsy: 4 mm skin punch biopsy (optional) is taken from the CKD-aP target area.
- 16. Tape stripping is conducted in all subjects from the CKD-aP target area.
- 17. "Therapies" refers to medications and therapies.

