3.4 Other Efficacy Endpoints

Other endpoints compare MC2-25 cream and MC2-25 vehicle and are:

- Mean change in WI-NRS recorded in the subject's diary from Baseline to Week 1, Week 4, and Week 8.
- Mean change in WI-NRS recorded during on-site visits from Baseline to Week 1, Week 4, Week 8 and Week 12.
- Mean change in Sleeploss due to Itch Numeric Rating Score (SI-NRS) from Baseline to Week 1, Week 4, Week 8 and Week 12.
- Mean change in Skin Dryness Numeric Rating Score (SD-NRS) from Baseline to Week 1, Week 4, Week 8 and Week 12.

Table 2WI-NRS, SI-NRS, SD-NRS scale and scores:

Worst Itch/ Worst Sleep Loss/ Worst Skin Dryness in last 24 hours											
0	1	2	3	4	5	6	7	8	9	10	
No Itch/										Worst	
No										Imaginable	
Sleeploss/										Itch/	
No Skin										Sleeploss/	
Dryness										Skin	
-										Dryness	

- Percentage of subjects who reported an improvement in Subject's Global Impression of Change (SGIC) (i.e. "Very much better", "Much better" or "A little better") will be reported for Week 1, Week 4, Week 8 and Week 12 for WI-NRS, SI-NRS and SD-NRS.

Note: SGIC will be summarized for all subjects (see Table 3). Categories 1 to 3 will be summarized as combined "Improvement in SGIC score". Categories 1 to 7 will be summarized individually.

Table 3SGIC for itch, sleep loss and skin dryness.

Choose response that best describes overall change in itch, sleep loss and skin dryness since you started taking the trial medication.

since jou sur ou withing the true incurations							
Improvement in	1	Very much better					
SGIC	2	Much better					
(1 to 3)	3	A little better					
	4	No change					
	5	A little worse					
	6	Much worse					
	7	Very much worse					

- Percentage of subjects who reported "an important improvement" in Subject's rating of importance of improvement (i.e., subjects who respond "Yes" to Question 1 in the 'Subjects rating of importance' assessment) for WI, SI, and SD at Week 1, Week 4, Week 8, and Week 12 or ET.
- Mean change in Subject's indication of CKD-aP treatment area size from Baseline to Week 4, Week 8 and Week 12.
- Mean change in 5D-Itch (Domain Scores and Total Score) from Baseline to Week 4, Week 8 and Week 12

The 5D-Itch consists of 5 domains numbered 1-5.

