5.2 Handling of Dropouts or Missing Data

5.2.1 Missing Data

For the primary and secondary efficacy endpoints, the primary estimands using the FAS, MFAS and PPS will use a treatment policy strategy for missing data. Missing data will be replaced using a multiple imputation (MI) approach. Note, missing data includes dropouts, empty data fields after dropout date will be handled as missing data regardless of reason for drop out. MI will be performed for all populations separately only if there is a difference in populations. Seed numbers for each endpoint will use the randomly generated 4-digit numbers from the table below. Other variables that are included in the imputation model will include treatment, site, country, visit, and key baseline characteristics such as age, gender, race, CKD stage stratum⁽¹⁾ at baseline, and systemic CKD-aP treatment status⁽²⁾ at baseline. Depending on the pattern of missingness, a 2-step process may be employed. If missing data points occur for an intermediate visit, they will be imputed first using a Markov Chain Monte Carlo (MCMC) method. As a result, a monotone missingness pattern will be obtained for the data to be fully imputed. The subsequent imputation will use general regression for continuous variables and logistic regression for categorical variables under the assumption data are missing at random to produce 20 imputed datasets where the remaining missing data are filled in using 20 separate sets of values. For the categorical secondary variables, the percentages will be calculated from the above imputed data.

- (1) CKD stage stratum at baseline= A. ≥40% of subjects must be on dialysis (HD or HDF) and must be CKD stages 4-5 (CKD stage 4-5 dialysis) B. ≥20% of subjects must Not be on dialysis and must be CKD stages 4-5 (CKD stage 4-5 non-dialysis) C. ≥20% of subjects must Not be on dialysis and must be CKD stage 3 (CKD stage 3)
- (2) Systemic CKD-aP treatment status at baseline will be flagged as "Yes" if prior/concomitant medication falls within one of the ATC groups provided in Section 6.3.2

Table 9 Population and Random Seed Number

Population	Random Seed Number
FAS	6529
MFAS	7631
PPS	9376

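### When an incomplete diary makes a weekly mean WI-NRS missing, the imputation model leaves out the on-site WI-NRS from the same visit: a small, cheaply recovered loss of information

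*SAP*

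**What the plan says.** The primary endpoint is the weekly mean of daily diary WI-NRS scores over the eight days ending at the visit. SAP 3.1 states: "If less than 4 observations are recorded in the 8 days expected, the weekly mean WI-NRS will be considered missing". Protocol 8.8.1 agrees, using the "average of minimum 4 WI-NRS values recorded once daily in the subject's diary", and Protocol inclusion criterion 6 applies the same minimum at Baseline.

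Missing weekly means are multiply imputed (SAP 5.2.1). Beyond the endpoint itself at other visits, the model is described thus: "Other variables that are included in the imputation model will include treatment, site, country, visit, and key baseline characteristics such as age, gender, race", followed by CKD stage stratum and systemic CKD-aP treatment status. Intermediate gaps are filled by MCMC and the rest by monotone regression, "under the assumption data are missing at random to produce 20 imputed datasets". Responder rates follow from the same datasets: "For the categorical secondary variables, the percentages will be calculated from the above imputed data".

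A second itch measurement exists at each of these visits. Protocol 7.9.1 requires that "the subject's WI-NRS must be evaluated at on-site visits at Screening, Baseline, Week 1, Week 4, Week 8, and Week 12", on the same 0–10 scale and with the same 24-hour worst-itch question. Footnote 7 to the SAP's Schedule of Events repeats it: "The WI-NRS must also be reported by the subject at on-site visits". In the SAP this score serves only as a separate endpoint (SAP 3.4: "Mean change in WI-NRS recorded during on-site visits from Baseline to Week 1" and later visits), summarised descriptively under SAP 5.5.3.

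**The concern.** A subject can attend Week 12, answer the worst-itch question in the clinic, and still have Week 12 itch treated as unknown because only three diary days were filled in. Neither the on-site answer nor the one to three diary scores that exist are listed as inputs to the imputation.

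Two things are at stake. The first is efficiency: imputed Week 12 values are more variable than they need to be, which affects the primary difference and the ≥3-point and ≥4-point responder rates, the last being the key secondary endpoint at Week 12. The second is the missing-at-random assumption. Without a same-visit itch report, it requires that skipping the diary does not depend on current itch once earlier itch and baseline factors are known. With the on-site score in the model, skipping may depend on current itch as far as that score captures it.

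**Working it through.** **1. The plan's own figure.** Inputs from Protocol 8.2: d = 1.5, s = 2.46, two-sided 5%, 2:1 allocation, 10% dropout.
- Vehicle n = (1 + 1/2) × (1.960 + 0.842)² × 2.46²/1.5² = 1.5 × 7.85 × 2.69 = 31.7, so 32. With 64 on cream the total is 96, and 96/0.90 = 106.7, so 107 against the stated 108.
- Power at 36/72: SE = 2.46 × √(1/36 + 1/72) = 0.502; 1.5/0.502 − 1.96 = 1.03, giving 84.8%. After 10% loss it is 80.9%.

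The sample size reproduces and is not in question.

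**2. One subject.** Take a subject with Baseline 7 and on-site Week 12 score 1, an on-site change of −6, whose Week 12 weekly mean is missing. From the documents: SD 2.46; vehicle change −2 (Protocol 2.2, which expects a reduction of at least 2), so cream −3.5 with d = 1.5. Assumed: the same arm mean at Week 8; Week 8 to Week 12 correlation ρ = 0.7; SD of on-site change 2.8; correlation q of the on-site score with the weekly mean 0.7 to 0.9.

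Without the on-site score, a draw has centre μ + ρ(x₈ − μ) and SD 2.46 × √(1 − 0.49) = 1.757, where x₈ is the Week 8 change. For cream with x₈ = −6 the centre is −3.5 + 0.7 × (−2.5) = −5.25, and the chance of missing −4 is 1 − Φ(1.25/1.757) = 24%. With x₈ = −0.5 the centre is −1.4 and the chance is 1 − Φ(−2.6/1.757) = 93%.

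Share of draws that miss the 4-point threshold (ranges run from q = 0.7 to q = 0.9):

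| Week 8 change | Cream, without | Cream, with on-site | Vehicle, without | Vehicle, with on-site |
|---|---|---|---|---|
| −6 | 24% | 12% to 4% | 32% | 14% to 6% |
| arm mean | 61% | 36% to 12% | 87% | 60% to 25% |
| −0.5 | 93% | 73% to 30% | 96% | 77% to 36% |

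With Week 8 at −6 and ρ from 0.5 to 0.85, the shares without the on-site score run from 36% to 11% (cream) and 50% to 14% (vehicle). For the 3-point threshold in the −6 row, cream goes from 10% to 3–0.3% and vehicle from 15% to 4–0.5%.

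**3. What reaches the primary comparison.** If a fraction m of Week 12 means is missing and the predictors explain R² of their variance, the effective sample fraction is about 1 − m(1 − R²). With m = 0.10 (assumed):
- without the on-site score, R² = 0.49: fraction 0.949, power 82.9%;
- with it, q = 0.8, R² = 0.733: fraction 0.973, power 83.8%;
- with it, q = 0.9, R² = 0.839: fraction 0.984, power 84.2%.

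The SE ratios are √(0.949/0.973) = 0.988 and √(0.949/0.984) = 0.982, a gain of 1–2%.

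**4. Simulation of the group comparisons.** 72 and 36 subjects, 20 imputations, Week 12 ANCOVA with Rubin's rules. Base-case assumptions: residual SD 2.2, visit-to-visit correlation 0.65, day-to-day SD 1.2, 10% attending Week 12 with an unscorable diary, and an on-site score equal to the Day 0 diary score except for a 30% chance of differing by 1.

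| Quantity | Without on-site | With on-site |
|---|---|---|
| SE, primary difference | 0.436 | 0.427 |
| SE, ≥4-point rate difference | 0.0893 | 0.0883 |
| Bias in rate difference, low-itch subjects skip more, 15% missing | −0.8 points | −0.4 points |
| Bias in primary difference, skipping depends on itch in one arm only, 15% missing | 0.13 | 0.05 |
| Bias in rate difference, same one-arm case | −3.0 points | −1.4 points |

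The SE gains are 2% and 1%. Varying the correlation (0.5–0.8), day-to-day SD (1.2–2.0) and missing share (10–15%), the primary SE gain was 1–4%. When skipping was unrelated to itch, bias was negligible under both models.

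**The case against.** A reader might infer from the single-subject example that nearly itch-free subjects are turned into non-responders, so that the key secondary endpoint is distorted. The documents do not support that. No rule assigns non-response; the subject's status varies over 20 random draws that are then pooled. Most draws miss the threshold only if Week 8 itch was still high or, under these assumptions, merely average for the arm. If Week 8 was already as good as Week 12, 24–32% miss it.

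Per-subject error is also the wrong yardstick. In the simulation, wrong ≥4-point status among the affected subjects falls from 28% to 18%, but multiple imputation adds random error on purpose. What counts is the bias and SE of the group difference, and these barely move when skipping is unrelated to itch. Even when low-itch subjects skip more in both arms, the bias of −0.8 points compares with an SE near 9 points.

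Three further objections stand. The 10–15% share has no source: Protocol 8.2 assumes 10% dropouts, which is a different group, and an on-site score cannot help a subject who did not attend. The protocol also works to keep diaries complete, with reminder calls and diary review at on-site visits. Finally, close agreement between one in-clinic rating and an eight-day home average is built into the simulation, not documented.

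What does not stand is that the predictor list is open and the score could simply be added later. The open wording covers baseline characteristics only, and an auxiliary variable should be named before unblinding.

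**Conclusion.** The point holds as a minor improvement. The 4-of-8 minimum is prespecified and consistent across both documents, and the imputation is valid if data are missing at random as stated. The weakness is that a closely related, already collected measurement from the same visit is left out, which costs some precision and makes missing-at-random a stronger assumption than the data require.

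The supportable size is a 1–4% smaller SE for the primary difference, about 1% for the ≥4-point rate difference, about one point of primary power at 10% missing, and removal of roughly half of any bias if skipping depends on current itch. The last matters most if skipping differs by arm. All of this rests on the assumed share of attendees with unscorable diaries and the assumed agreement of the two scores, so the effect in this trial cannot be fixed from the documents.

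The point covers the weekly mean and the 3- and 4-point rates. A reader might extend it to complete response, but SAP 3.3 defines that on non-missing scores and states no four-score minimum.

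**What to change.** In SAP 5.2.1, add the on-site WI-NRS at each visit as an auxiliary variable in the imputation model for weekly mean WI-NRS, for the FAS and MFAS. State that it is imputed jointly in the MCMC step when the visit was not attended, and that it is ordered before the same-visit weekly mean in the monotone step. For the hypothetical-strategy analysis, set it to missing after the start of prohibited therapy, as is already done for WI-NRS data under SAP 5.2.3. Leave the endpoint, the 4-of-8 rule, the MMRM and the GEE model as they are.

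The cost is a short SAP addition and one existing variable in the imputation code, with no new data. The downside is a somewhat larger imputation model, in one that already carries site (about 26 planned) for 108 subjects, with an auxiliary variable that has missing values of its own.

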3.2 Key Secondary Efficacy Endpoint

The key secondary efficacy endpoint is to compare percentage of subjects obtaining a \geq 4-point improvement in weekly mean WI-NRS recorded in the subjects' diaries from Baseline to Week 12 between MC2-25 cream and MC2-25 vehicle.

3.3 Secondary Efficacy Endpoints

The secondary efficacy endpoints will compare MC2-25 cream and MC2-25 vehicle for following points:

- Percentage of subjects obtaining a \geq 4-point improvement in weekly mean WI-NRS recorded in the subjects' diaries from Baseline to Week 1, Week 4 and Week 8.
- Percentage of subjects obtaining $a \ge 3$ -point improvement in weekly mean WI-NRS recorded in the subjects' diaries from Baseline to Week 1, Week 4, Week 8 and Week 12.
- Percentage of subjects obtaining a complete response in weekly WI-NRS recorded in the subjects' diaries from Baseline to Week 1, Week 4, Week 8 and Week 12. Complete response is defined as scores equal to 0 or 1 in \geq 80% of the non-missing WI-NRS values recorded in the subjects' diaries 7 days prior to and including the scheduled in clinic visits.
- Percentage of subjects obtaining an alternative complete response in weekly WI-NRS recorded in the subjects' diaries from Baseline to Week 1, Week 4, Week 8 and Week 12. Alternative complete response is defined as scores equal to 0 or 1 in ≥ 70% of the non-missing WI-NRS values recorded in the subjects' diaries 7 days prior to and including the scheduled in clinic visits.

3.4 Other Efficacy Endpoints

Other endpoints compare MC2-25 cream and MC2-25 vehicle and are:

- Mean change in WI-NRS recorded in the subject's diary from Baseline to Week 1, Week 4, and Week 8.
- Mean change in WI-NRS recorded during on-site visits from Baseline to Week 1, Week 4, Week 8 and Week 12.
- Mean change in Sleeploss due to Itch Numeric Rating Score (SI-NRS) from Baseline to Week 1, Week 4, Week 8 and Week 12.
- Mean change in Skin Dryness Numeric Rating Score (SD-NRS) from Baseline to Week 1, Week 4, Week 8 and Week 12.

Table 2WI-NRS, SI-NRS, SD-NRS scale and scores:

Worst Itch/ Worst Sleep Loss/ Worst Skin Dryness in last 24 hours											
0	1	2	3	4	5	6	7	8	9	10	
No Itch/										Worst	
No										Imaginable	
Sleeploss/										Itch/	
No Skin										Sleeploss/	
Dryness										Skin	
-										Dryness	

- Percentage of subjects who reported an improvement in Subject's Global Impression of Change (SGIC) (i.e. "Very much better", "Much better" or "A little better") will be reported for Week 1, Week 4, Week 8 and Week 12 for WI-NRS, SI-NRS and SD-NRS.

Note: SGIC will be summarized for all subjects (see Table 3). Categories 1 to 3 will be summarized as combined "Improvement in SGIC score". Categories 1 to 7 will be summarized individually.

Table 3SGIC for itch, sleep loss and skin dryness.

Choose response that best describes overall change in itch, sleep loss and skin dryness since you started taking the trial medication.

since jou sur ou withing the true incurations							
Improvement in	1	Very much better					
SGIC	2	Much better					
(1 to 3)	3	A little better					
	4	No change					
	5	A little worse					
	6	Much worse					
	7	Very much worse					

- Percentage of subjects who reported "an important improvement" in Subject's rating of importance of improvement (i.e., subjects who respond "Yes" to Question 1 in the 'Subjects rating of importance' assessment) for WI, SI, and SD at Week 1, Week 4, Week 8, and Week 12 or ET.
- Mean change in Subject's indication of CKD-aP treatment area size from Baseline to Week 4, Week 8 and Week 12.
- Mean change in 5D-Itch (Domain Scores and Total Score) from Baseline to Week 4, Week 8 and Week 12

The 5D-Itch consists of 5 domains numbered 1-5.

- Domains 1-3 are single item (question) domains exploring the Duration (Duration domain), Degree (Degree domain) and Direction (Direction domain) of Itch. For each of domains 1-3 the domain score is equal to the value indicated below the response choice (range 1–5).
- Domain 4 (Disability domain) includes four items (questions) assessing the impact of itching on daily activities: sleep, leisure/social activities, housework/errands and

work/school). For domain 4 the score is achieved by taking the highest score on any of the four items (range 1-5).

- Domain 5 (Distribution domain) assesses the number of affected body parts out of 16 possible options. For domain 5 the score is obtained by tallying the number of affected body parts and the sum is sorted into five scoring bins: sum of 0-2 = score of 1, sum of 3-5 = score of 2, sum of 6-10 = score of 3, sum of 11-13 = score of 4, and sum of 14-16 = score of 5 (range 1-5).
- The total score is achieved by summing together the 5 domain scores and can therefore range between 5 (no pruritus) and 25 (most severe pruritus).
- Continuous descriptive statistics will be provided for all individual domains except Domain 5 from Baseline to Week 4, Week 8 and Week 12.
- Mean change in 5D-Itch Total Score will be presented using continuous descriptive statistics from Baseline to Week 4, Week 8 and Week 12.

1. Duration	During the last 2 weeks, how many hours a day have you bee itching?						
	Less than 6hrs a day	6-12hrs/ day	12-18hrs/ day	18-23hrs/ day	All day		
	1	2	3	4	5		
2. Degree	Please rate	the intensity of	of your itching	g over the pa	st 2 weeks		
	Not	Mild	Moderate	Severe	Unbearabl		
	Present				e		
	1	2	3	4	5		
3. Direction	Over the p	ast 2 weeks l	has your itch	ing got bette	er or worse		
	compared t	o the previous	s month?				
	Completel	Much	Little bit	Unchanged	Getting		
	y resolved	better, but	better, but		worse		
		still present	still present				
	1	2	3	4	5		
4. Disability	Rate the im	pact of your i	tching on the	following act	tivities over		
	the last 2 w	eeks		1			
• Sleep	Never	Occasionall	Frequently	Delays	Delays		
	affects	y delays	delays	falling	falling		
	sleep	falling	falling	asleep and	asleep and		
		asleep	asleep	occasionall	frequently		
				y wakes me	wakes me		
				up at night	up at night		
	1	2	3	4	5		
• Leisure/	Never	Rarely	Occasionall	Frequently	Always		
social	affects this	affects this	y affects	affects this	affects this		
• Housewor	activity	activity	this activity	activity	activity		
k/ Errands							
• Work/							
Studies							
	1	2	3	4	5		

Table 45D- Itch Questionnaire

5. Distribution	Mark whether itching has been present in the following part of your body over the last 2 weeks. If a body part is not listed choose the one that is closest anatomically								
Head/ Scalp		Top of feet/ Toes							
Face		Soles							
Chest		Palms							
Abdomen		Top of hands/ fingers							
Back		Forearms							
Buttocks		Upper arms							
Thighs		Point of contact w/ clothing							
Lower Legs		Groin							

- Mean change in Skindex-10 (Domain Scores and Total Score) from Baseline to Week 4, Week 8 and Week 12
 - The Skindex-10 consists of 10 questions (beginning with "During the past week, how often have you been bothered by.....") exploring the impact of itch on 3 domains (disease, mood/emotional distress and social functioning) with a 1 week recall period.
 - Each question must be scored on a 7-point scale ranging from 0 (never bothered) to 6 (always bothered).
 - The domain scores are the sums of the following: disease domain (questions 1 to 3), mood/emotional distress domain (questions 4 to 6), and social functioning domain (questions 7 to 10).
 - The total score is the sum of the numeric value of each answered question. The total score ranges from 0 to 60.
 - Continuous descriptive statistics will be presented for individual questions (Q1- Q10).
 - Domains (1) Disease (Q1- Q3), Domain (2) Mood/ Emotional Distress (Q4 Q6) and Domain (3) Social Functioning (Q-7 - Q10) will be presented using continuous descriptive statistics.
 - Mean change in Total Skindex-10 Score will be summarized descriptively from Baseline to Week 4, Week 8 and Week 12.

Durin	During the past week, how often have you been bothered by:										
		0	1	2	3	4	5	6			
		(Never						(Always			
		bothered)						bothered)			
1.	Your itching										
2.	The										
	persistence/										
	reoccurrence of										
	your itching										
3.	The appearance										
	of your skin										
	from scratching										
4.	Frustration										
	about your										
	itching										

Table 5Skindex-10 Questionnaire

5. Being annoyed about your itching				
6. Feeling depressed about your itching				
7. Feeling embarrassed about your itching				
8. The effects of your itching in interactions with other				
9. The effects of your itch on your desire to be with people				
10. The effect of your itching making hard to work or do things you enjoy				

- Mean change in EQ-5D-5L (Visual analogue scale [VAS] and Index value) from Baseline to Week 4, Week 8 and Week 12

Note: EQ-5D-5L Index Value (calculated using EQ5D5L algorithm) and VAS (i.e., Your Health Today Question) will be analyzed separately.

EQ-5D-5L Index Value:

The EQ-5D-5L descriptive system comprises five dimensions (5D) (MOBILITY, SELF-CARE, USUAL ACTIVITIES, PAIN / DISCOMFORT and ANXIETY / DEPRESSION), each dimension has five response levels (5L): no problems, slight problems, moderate problems, severe problems, unable to/extreme problems. The respondent is asked to indicate his/her health state by checking the box next to the most appropriate response level for each of the five dimensions.

A unique health state is defined for each subject by combining the response levels from each of the five dimensions. EQ-5D-5L health states can thus be summarized using the 5-digit code summary number, which reflects how good or bad a health state is according to the preferences of the general population of a country/region.

To compare two or more health states with each other or to understand which dimension has a greater impact on health-related quality of life (HRQoL), an index value derived from a set of utility values is given to each unique health state. This index value is needed to summarize how good or bad each health state is on a scale anchored at 1 (full health) and 0 (a state equivalent

to dead). Values less than 0 represent health states considered to be or modelled as worse than dead.

The utility values are based on the views and preferences of the general public and numerous country-specific value sets were produced by EuroQol Research Organization for EQ-5D-5L. The EQ-5D-5L index value for this study will be calculated for patients in United Kingdom using English Population Value Set, and for Germany, Hungary and Poland, using German population value set, Hungarian population value set, and Polish population value set respectively as presented in Table 6.

An index value thus calculated based upon below mentioned value sets can range anywhere between -1 and 1.

Table 6	EQ 5D 5L Values sets for U	Jnited Kingdom (UK),	Germany (GR), Hungary (HR)
and Poland (I	PL)		

Activity	Scale	Score	UK Value	GR Value	HR Value	PL Value
			Set	Set	Set	Set
Mobility	I have no problem in walking	1	0	0	0	0
	I have slight problem in walking	2	0.058	0.026	0.035	0.025
	I have moderate problem in walking	3	0.076	0.042	0.054	0.034
	I have severe problem in walking	4	0.207	0.139	0.174	0.126
	I am un able to walk	5	0.274	0.224	0.192	0.314
 	x 1 1 1 1	1				0
Self Care	I have no problem in washing or dressing myself	1	0	0	0	0
	I have slight problem in washing or dressing myself	2	0.050	0.050	0.045	0.031
	I have moderate problem in washing or dressing myself	3	0.080	0.056	0.044	0.047
	I have severe problem in washing or dressing myself	4	0.164	0.169	0.152	0.111
	I am un able to wash or dress myself	5	0.203	0.260	0.125	0.264
Usual Activity	I have no problem in performing usual activities	1	0	0	0	0

	I have slight problem in performing usual activities	2	0.050	0.036	0.035	0.023
	I have moderate problem in performing usual activities	3	0.063	0.049	0.050	0.040
	I have severe problem in performing usual activities	4	0.162	0.129	0.132	0.097
	I am un able to perform usual activities	5	0.184	0.209	0.059	0.205
Pain/ Discomfort	I have no pain and discomfort	1	0	0	0	0
	I have slight pain and discomfort	2	0.063	0.057	0.043	0.030
	I have moderate pain and discomfort	3	0.084	0.109	0.030	0.050
	I have severe pain and discomfort	4	0.276	0.404	0.215	0.261
	I am extreme pain and discomfort	5	0.335	0.612	0.123	0.575
Anxiety/ Depression	I have no anxiety/ depression	1	0	0	0	0
	I have slight anxiety/ depression	2	0.078	0.030	0.040	0.018
	I have moderate anxiety/ depression	3	0.104	0.082	0.053	0.029
	I have severe anxiety/ depression	4	0.285	0.244	0.168	0.108
	I have extreme anxiety/ depression	5	0.289	0.356	0.079	0.232

Overall Utility Value Total (UVT)= Mobility UVT+ Self Care UVT+ Usual Activity UVT+ Pain/ Discomfort UVT + Anxiety/ Depression (UVT) **EQ5D5L Index=** 1, Overall UVT (rounded to three desired points)

EQ5D5L Index= 1- Overall UVT (rounded to three decimal points)

EQ-5D-5L VAS Score

The VAS records the subject's overall current health on a vertical VAS where the endpoints are labelled "(100) The best health you can imagine" and "(0) The worst health you can imagine." The VAS provides a quantitative measure of the subject's perception of his/her overall health, higher score indicating better quality of life.

Table 7EQ-5D-5L VAS

Your Health	On a rate of 0 to 100 how is your health today, 0 being worst	0 - 100
today	and 100 being best	

Mean change in EQ-5D-5L Index score and VAS score will be presented descriptively from Baseline to Week 4, Week 8 and Week 12.

- Percentage of subjects obtaining a \geq 2-step improvement in Clinician's Global Assessment (CGA) for the following endpoints from Baseline to Week 1, Week 4, Week 8 and Week 12:
 - Skin dryness
 - Skin signs of itch
 - Overall skin appearance (The overall CGA of skin appearance is defined based on the intensity
 of the individual signs skin dryness and skin signs of itch. In case of difference in intensity of
 skin dryness and skin signs of itch then the worst intensity shall prevail in the overall CGA of
 skin appearance)
- Percentage of subjects obtaining a \geq 2-step improvement in Clinician's Targeted Assessment (CTA) for the following endpoints from Baseline to Week 1, Week 4, Week 8 and Week 12.
 - Skin dryness
 - Skin signs of itch
 - Overall skin appearance (The overall CTA of skin appearance is defined based on the intensity
 of the individual signs skin dryness and skin signs of itch. In case of difference in intensity of
 skin dryness and skin signs of itch then the worst intensity shall prevail in the overall CTA of
 skin appearance)

CGA/ CTA Score	Skin Dryness Descriptions	Skin Signs of Itch
		Description
Clear	No skin dryness	No active signs of itch
Almost Clear	Barely perceptible skin dryness	Barely recognizable active skin
		signs of itch
Mild	Easily perceptible skin dryness	Easily recognizable active skin
		signs of itch
Moderate	Moderate skin dryness	Moderate active skin signs of
		itch
Severe	Marked skin dryness	Marked active signs of itch

Table 8CGA/ CTA Score

- The mean change in weekly mean WI-NRS recorded in the subject's diary will be assessed within both arms (MC2-25 cream and MC2-25 vehicle) for change from Baseline to Week 1, Week 4, Week 8 and Week 12.

